10.1.3 Procedure for handling missing data

The safety assessment will include in the analysis all subjects who have been exposed to any of the interventions, regardless of the visit at which they were eliminated from the study (ITT; intention-to-treat population).

10.1.4 Deviations from the statistical analysis plan

According to the sample size calculation to meet the study objective, 28 evaluable subjects (14 cases per arm) are required. If this number is not met due to a loss of subjects exceeding the 20% threshold established in this protocol (loss to follow-up or withdrawal from ICF), the sponsor may substitute these subjects to balance the treatment groups.

The results obtained from the replaced subjects will continue to be used for safety analysis and will be part of the ITT.

10.1.5 Subjects included in the analysis

Those subjects who complete all their visits will be included in the statistical analysis to meet the study objective (PP; per-protocol population).

The variables, method and scales for their measurement are described in detail below.

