3.2 Specific objectives

- To compare the safety of OVD PRO-149 versus Healon® EndoCoat in cataract phacoemulsification surgery and intraocular lens implantation, through changes in pre and postoperative CEC density.
- To compare the safety of OVD PRO-149 versus Healon® EndoCoat in cataract phacoemulsification surgery and intraocular lens implantation, through changes in IOP.

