5.2 Criteria for elimination and/or substitution of subjects

5.2.1 Elimination criteria

- Withdrawal of informed consent.
- Major deviation from the protocol that could impact the integrity of the results.
- Presentation of an adverse event, whether or not related to the investigational product, which, in the opinion of the PI and/or the sponsor, could affect the subject's ability to safely continue the study procedures.
- Non-tolerability or hypersensitivity to any of the compounds used during the tests (fluorescein, lissamine green, tetracaine).
- Non-tolerability or hypersensitivity to any of the investigational drugs.

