7.3 Randomization and blinding

Treatment allocation/randomization will be performed centrally using an integrated web-based response system (IWRS). There are two treatment groups. Participants will be randomly assigned 1:1 to treatment with PRO-149 or Healon® EndoCoat, with equal probability of being assigned to either treatment.

After signing the ICF, the subject will receive a patient number under which all information will be coded pseudo-anonymously during collection and completely anonymized during analysis.

The generation will be carried out by a third party, authorized by Laboratorios Sophia, S.A. de C.V., through its electronic system, using a list of random numbers (SAS Institute Inc, Cary, NC, USA). Information corresponding to this third party will be found on file.

This is an open-label study, meaning there is no blinding, except for the statistical analysis. The investigational products will be identified by labels that comply with current and applicable regulations. These labels must contain, at a minimum, the following:

- Name, address and telephone number of the sponsor.

- Pharmaceutical form and route of administration.
- Number of doses.
- Batch number.
- Legend "Exclusively for clinical studies"
- Expiration date.

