10.1.2 Data interpretation

The results of continuous quantitative variables will be presented in measures of central tendency: mean, standard deviation and ranges.

KS and SW tests will be performed, as applicable, to determine whether the distribution presents normality in the results obtained in each study group. [44]

If normality of the data is observed ($p > 0.05$; for KS and SW), the statistical analysis of the continuous quantitative variables to find significant differences (p) will be as follows:

- Intra-group analysis: will be determined using the Student's t-test for repeated measures.
- Between-group analysis: differences between groups will be analyzed using Student's t-test for independent groups.

For $p < 0.05$ in KS and SW, the statistical analysis of continuous quantitative variables to find significant differences (p) will be as follows:

- Intra-group analysis: will be determined using the Wilcoxon rank test. [45]
- Between-group analysis: differences between groups will be analyzed using the Mann-Whitney U statistic.

The level of difference to consider significance will be an α of 0.05 or less [46].

The results of the nominal and ordinal qualitative variables will be presented in frequencies, proportions and percentages.

Statistical analysis to identify significant differences in qualitative variables will be performed by creating 2x2 contingency tables and will be carried out as follows:

- Intra-group differences: will be determined by the McNemar test [47], which is applied to 2x2 contingency tables with a dichotomous trait and pairs of matched subjects to determine whether the marginal frequencies of row and column are equal (marginal homogeneity).
- Difference between groups: Differences between groups will be analyzed using Pearson's X^2 test or Fisher's exact test when expected values are less than 5.

The level of difference to consider significance will be an α of 0.05 or less.

For the reporting of adverse events, participants who were randomly assigned to an intervention group after application of the investigational product will be considered.

The final results report will be displayed in tables or graphs, as appropriate.

The investigational product will be considered safe when there are no clinical and statistical differences in all primary outcome variables, with respect to its comparator (Healon EndoCoat®).

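### The rule that decides safety names no analysis set. On the likelier reading (completers only), recorded IOP from subjects eliminated for an adverse event may be left out.

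*Combined protocol and SAP*

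**What the plan says.** The primary objective (3.1) is the safety of PRO-149 against Healon EndoCoat. Section 3.2 splits it into two comparisons, one on CEC density and one on IOP; the second reads "To compare the safety of OVD PRO-149 versus Healon® EndoCoat in cataract phacoemulsification surgery and intraocular lens implantation, through changes in IOP". Section 7.4.1 lists the same two measures as the primary outcome variables.

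Four places say who is analysed:

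- 10.1.5: "Those subjects who complete all their visits will be included in the statistical analysis to meet the study objective (PP; per-protocol population".
- 10.1.3: the safety assessment takes in "all subjects who have been exposed to any of the interventions, regardless of the visit at which they were eliminated from the study", labelled intention-to-treat (ITT).
- 10.1.4: for the study objective, "28 evaluable subjects (14 cases per arm) are required"; for subjects who are substituted, "The results obtained from the replaced subjects will continue to be used for safety analysis and will be part of the ITT".
- 6.4: subjects below 60% adherence to the post-operative drops are assigned to the ITT population. Section 10.1.5 contains no adherence condition.

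The decision rule is in 10.1.2: "The investigational product will be considered safe when there are no clinical and statistical differences in all primary outcome variables". It does not say in which subjects.

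On who may leave, one ground for elimination in 5.2.1 is "an adverse event, whether or not related to the investigational product, which, in the opinion of the PI and/or the sponsor, could affect"; what must be in doubt is whether study procedures can go on safely. Section 7.3 adds: "This is an open-label study, meaning there is no blinding, except for the statistical analysis".

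**The concern.** Because the objective is itself safety, 10.1.3 and 10.1.5 appear to give two different sets to the same question, and the rule that settles the question picks neither. Completion of visits is not independent of safety here: one route out of the trial is an adverse event, and the judgement is made by an investigator or sponsor who can know which product was used.

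The rule in 10.1.2 treats the absence of a difference as safety. If PRO-149 eyes with raised pressure were to leave the completer set more often than comparator eyes, the IOP comparison would be drawn toward a safe conclusion. If comparator eyes left more often, it would be drawn the other way. With no set named, the choice could also be settled after the results of both are available.

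**Working it through.** No planned figure is in dispute, so the check sets the sections side by side and counts what each set keeps.

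**1. Which set does the plan mean for the primary variables?** Section 10.1.4 ties the study objective to evaluable subjects and separately sends substituted subjects to the safety analysis and ITT. Section 10.1.5 uses the same tie to the study objective and calls that set per-protocol. Read together, they point to per-protocol for CEC density and IOP, and ITT for wider safety reporting. Against this, 10.1.3 speaks of the safety assessment without limiting it to adverse events, and adverse-event reporting already has its own population sentence in 10.1.2. The per-protocol reading is the likelier one, but the plan does not state it.

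**2. What is recorded before a subject leaves?** From the schedule (1.3) and Table 3, post-operative IOP is measured on Day 1, Day 8 and Day 29 (3 values). Post-operative CEC density is measured only on Day 29 (1 value).

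| Last scheduled visit attended | Post-op IOP recorded | Post-op CEC recorded | In 10.1.3 set | In 10.1.5 set |
|---|---|---|---|---|
| Day 1 | 1 of 3 | 0 of 1 | yes | no |
| Day 8 | 2 of 3 | 0 of 1 | yes | no |
| Day 29, all visits attended | 3 of 3 | 1 of 1 | yes | yes |

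A non-completer therefore takes 1 or 2 recorded IOP values out of the completer comparison. For CEC density the two sets hold the same post-operative data for early leavers: none.

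**3. Does elimination for an adverse event mean exclusion?** Not necessarily. Section 10.1.5 turns on completing visits, and 5.5 continues follow-up of subjects withdrawn for an adverse event until it resolves. A subject followed through the final visit could still qualify. Section 5.5 does not say whether the final-visit specular microscopy and tonometry are then recorded as study data.

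**4. Are such subjects replaced?** Section 5.2.2 names only withdrawal of consent and loss to follow-up as grounds for replacement. On that text, a subject eliminated for an adverse event who does not complete simply reduces the completer set.

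**5. Can the loss be sized?** The planned numbers are 14 evaluable per arm, and 14 / (1 - 0.20) = 17.5, rounded up to 18. The tolerated shortfall is 18 - 14 = 4 per arm. Section 10.1.4 describes that allowance as covering loss to follow-up and withdrawal of consent, so it gives no ceiling for eliminations due to adverse events. The documents give no elimination rate and no IOP values for eliminated subjects, so no bias can be calculated. How the 14 was derived is a separate matter, and nothing here depends on it.

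**The case against.** The strongest reply is that the plan does largely name the set: per-protocol for the primary variables, ITT for the rest. That reading is coherent, and the point is written on it. It does not remove the problem, because it is the reading under which recorded IOP may be left out.

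A second reply is that an equivalence hypothesis (3.5) gives per-protocol a legitimate place, since an analysis of all subjects can dilute a real difference; 6.4 also treats adherence to the drops as critical because inflammation could confound the study variables. This stands. It is why the fix keeps both sets and does not make all exposed subjects the sole primary set.

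A third is that 10.1.1 blinds the statistical staff to group. That limits selective choice of a set, but it does not reach the person who decides on elimination.

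Three stronger readings are tempting and are not supported:

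- **That high pressure removes a subject.** Section 2.2.2 cites IOP of 30 mmHg or more in 10.5% of Healon EndoCoat subjects, so a reader might expect 18 x 0.105 = 1.9 eyes per arm to drop out. Section 7.4.4.2 makes such a peak reportable, but 5.2.1 does not list it as a ground for elimination, and 6.3 permits pressure-lowering drugs after the first safety visit. Likewise, under 7.4.4.1 a CEC change alone is not an adverse event.
- **That up to 4 per arm, with a matching share of all IOP readings, would be discarded for adverse events.** The 4 belongs to a different allowance, and a pooled share of readings corresponds to no planned test and does not measure bias.
- **That the bias favours PRO-149, or that the data are lost altogether.** The direction is unknown, and 10.1.3 and 10.1.4 keep these subjects in ITT.

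**Conclusion.** The point holds in limited form. The plan does not expressly reconcile 10.1.3 with 10.1.5 for primary variables that are themselves the safety measures, and the rule in 10.1.2 names no set. On the likelier reading, a subject eliminated for an adverse event who does not complete all visits may be absent from the IOP comparison that decides safety, with 1 or 2 recorded post-operative values unused there. This assumes that at least one such subject occurs after Day 1; the documents do not say how often that would happen. The effect on the result cannot be quantified in size or direction. The set makes no difference to recorded post-operative CEC density in early leavers. The adherence threshold in 6.4 is a further gap, because it implies a per-protocol condition that 10.1.5 omits. This should be fixed before analysis: with 18 subjects per arm, few exclusions are needed to matter, and the remedy is nearly free.

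**What to change.** - **IOP.** State that the rule in 10.1.2 is applied by visit in all randomised subjects in whom the device was used, analysed as randomised and with all recorded values, and also in the per-protocol set. A conclusion of safety requires both to agree.
- **CEC density.** State that it is analysed in all exposed subjects with a final-visit value, with the number of missing values and the reasons reported by arm.
- **Per-protocol.** Define it once, reconciling 10.1.3, 10.1.5 and 6.4, and say whether the 60% adherence threshold is part of it.
- **Withdrawn subjects.** Reconcile 5.5 with 5.2.1 on whether the already scheduled final-visit measurements are recorded for subjects withdrawn for an adverse event. This concerns data recording only; follow-up care is for the clinical team.

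Cost: revised wording and a little more analysis. IOP estimates in all exposed subjects may be slightly more variable, and requiring agreement makes the route to a safety conclusion somewhat stricter.

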10.2 Sample size calculation

10.2.1 Number of subjects calculated

36 evaluable subjects were estimated (18 subjects per arm, one eye per subject).

10.2.2 Justification of the sample calculation

Although there are no references on sample size calculation for pilot studies, it was considered appropriate to perform the calculation based on the clinical study by Storr-Paulsen et al [48], who compared the influence of three OVDs of 1%, 2% and 3% SH on corneal endothelial cell count during cataract surgery up to three months postoperatively. All three OVDs showed a decrease in postoperative cell count, for SH-1% it was 18.46%, for SH-2% it was 18.03% and for SH-3% it was 6.97%. [48]

The percentage decrease in dispersive OVD at 3% SH was considered. The sample size was calculated using the equation for an equivalence ratio [49], which is useful when we want to test whether a ratio p , is different from a standard reference value, p_0 . In this case, we want to test that PRO-149 is equivalent to its comparator (Healon® EndoCoat). Here the test falls on PRO-149; that is, equivalence is represented by the alternative hypothesis (H_1), rather than the null hypothesis (H_0).

Working hypothesis for calculating the sample size:

$$H_0: |P - P_0| \geq \delta$$
$$H_1: |P - P_0| < \delta$$

Considering an $\alpha = 0.05$ corresponding to the type I error (95% confidence level), a power (β) = 0.20 corresponding to the type II error (80% power) and a test margin (δ) of 5%. The calculation to estimate the sample size was performed using an online tool (*Sample size calculators*, <http://powerandsamplesize.com>), following the following equations:

$$n = p(1-p) \left(\frac{Z_{1-\alpha} + Z_{1-\beta/2}}{|p - p_0| - \delta} \right)^2$$

$$1 - \beta = 2[\Phi(z - z_{1-\alpha}) + \Phi(-z - z_{1-\alpha})] - 1, z = \frac{|p - p_0| - \delta}{\sqrt{\frac{p(1-p)}{n}}}$$

Where:

n: sample size,

p₀: comparison value,

Φ: function of the standard normal distribution

Φ⁻¹: normal standard quantile function

α: Type I error

β: Type II error (1-β is the power)

δ: test margin.

According to the previous calculation, the result was 14 cases (eyes) per arm; this calculation was increased by 20% to account for potential losses. The total sample size required is 18 cases (eyes) per treatment arm, a total of 36 cases. This calculation is consistent with the sample size used in similar clinical studies where OVDs were employed. [50, 51, 52]

11. Ethical considerations

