2.2.2 Safety of the investigational product

In the same clinical study described above, safety was evaluated by the cumulative rate of intraocular pressure (IOP) peaks ≥ 30 mmHg and the presence of adverse events (AEs).

The results demonstrated that the percentage of subjects with IOP spikes in the Healon® EndoCoat group was not higher than that in the Viscoat® group (cumulative percentage of subjects with IOP ≥ 30 mmHg during the study ($p = 0.0003$, $\delta = 0.13$, 90% confidence interval [-1.74, 7.72]).

Surgical complications reported were 3% (6/200) in the Healon® EndoCoat group and 8% (16/200) in the Viscoat® group.

Regarding AEs, 39 subjects reported an AE during the study. None of these were considered unexpected. Ninety-two percent of the AEs were IOP ≥ 30 mmHg; the incidence of this AE was 10.5% in the Healon® EndoCoat group and 7.5% in the Viscoat® group. The three AEs that did not correspond to an increase in IOP included: one subject in the Healon® EndoCoat group who developed cystoid macular edema (requiring treatment) and two subjects in the Viscoat® group: one subject who required IOL exchange for haptic damage and one who underwent removal of an ocular surface foreign body. None of the above AEs were considered related to OVD use. [21]

List of incidents or adverse reactions reported with a 3% sodium hyaluronate viscoelastic or with the use of intraocular sodium hyaluronate: [21] [22]

- Eye inflammation (iritis, hypopyon, endophthalmitis)
- Increased intraocular pressure
- Corneal edema
- Secondary glaucoma
- Corneal decompensation

All of the described incidents or adverse reactions may potentially occur with the use of PRO-149 or Healon® EndoCoat. [21] [22]

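### The sample size and 80% power rest on endothelial cell loss alone, so they do not support a safety conclusion that needs both cell density and IOP; at the stated 5% margin the 80% fails for cell loss too

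*Combined protocol and SAP*

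**What the plan says.** Section 7.4.1 names two primary outcomes, change in CEC density and IOP, and section 3.2 has a specific objective for each. Table 3 treats IOP as a continuous variable in mmHg, compared by t-test or Mann-Whitney.

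The sample size in section 10.2.2 draws on one outcome. It reports cell losses from a published comparison of three hyaluronate OVDs ("for SH-2% it was 18.03% and for SH-3% it was 6.97" per cent) and then states: "The percentage decrease in dispersive OVD at 3% SH was considered". It sets α at 0.05, "corresponding to the type I error (95% confidence level"), and β at 0.20, "corresponding to the type II error (80% power) and a test margin (δ) of 5" per cent. The outcome of the calculation: "the result was 14 cases (eyes) per arm; this calculation was increased by 20% to account for potential losses". That leads to 18 per arm, 36 in all.

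Section 10.1.4 then links the number to the trial's purpose: "According to the sample size calculation to meet the study objective, 28 evaluable subjects (14 cases per arm) are required". Section 10.1.2 gives the pass rule: the product is safe when there are "no clinical and statistical differences in all primary outcome variables" against the comparator. The tests listed there are tests for a difference, whereas the hypotheses in sections 3.5 and 10.2.2 are equivalence hypotheses.

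**The concern.** The conclusion needs both outcomes to pass, but the sample size was worked out for one. IOP enters section 10.2.2 with no expected value, spread or margin, and none is given for this trial elsewhere. Ethics committees and the regulator would read sections 10.2.2 and 10.1.4 together as saying that 14 evaluable eyes per arm answer the study question with 80% power. If no such figure exists for the two-outcome conclusion, and the CEC figure is itself wrong, a finding of safety would carry an assurance that the design does not provide.

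**Working it through.** **1. The plan's own figure.** Inputs from section 10.2.2: α = 0.05, β = 0.20, δ = 0.05, SH-3% loss 6.97%. The section does not state p and p0 separately; I take p = p0 = 0.0697, the case of equal products. Its formula is n = p(1−p)[(z₁₋α + z₁₋β/₂)/(|p−p0| − δ)]².

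- p(1−p) = 0.0697 × 0.9303 = 0.0648; (1.645 + 1.282)² ≈ 8.56.
- δ = 0.05: 0.0648 × 8.56/0.0025 ≈ 222.1, so **223**, not 14.
- δ = 0.20: 0.0648 × 8.56/0.04 ≈ 13.9, so **14**.
- Other choices of p0 (0, 0.05, 0.1803, 0.1846) and of the z-terms, all at δ = 0.05, give 95 to 1,756. None gives 14.
- The section's power formula at δ = 0.05 returns −0.62 for n = 14 and −0.57 for n = 18, which means effectively no power. At δ = 0.20 and n = 14 it returns 0.804.
- The loss step is consistent: 14/(1 − 0.20) = 17.5, so 18.

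**2. Cross-check of CEC as a mean.** Section 2.2.1 gives a 90% CI of 0.23 to 4.33 points for the difference in mean percentage change between two groups of 200. SE = (4.33 − 0.23)/(2 × 1.645) = 1.246, and SD = 1.246/√(2/200) ≈ 12.5 points. This assumes that all 400 were analysed and that the 3-month spread applies at this trial's final visit (day 29). With a 5-point margin, two one-sided tests have power below 0.1% at 14 or 18 per arm. About 107 per arm are needed for 80%.

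**3. Two outcomes, equivalence reading.** The chance of passing both tests cannot exceed the smaller of the two single chances. If each had 80% power, the joint figure would be:

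| Correlation | Joint power |
|---|---|
| 0 | 0.64 |
| 0.3 | 0.65 |
| 0.5 | 0.67 |
| 0.8 | 0.71 |
| 1 | 0.80 |

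This is illustrative. On assumed IOP values, power at 14 per arm runs from 0.00 (SD 5, margin 2 mmHg) to 0.999 (SD 2.5, margin 5 mmHg). The documents do not say where in that range the trial lies.

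**4. Two outcomes, the rule as written.** Take the statistical half of the rule as two non-significant tests at 5%, with one IOP comparison.

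- Identical products: 0.95 × 0.95 ≈ 0.90 if independent, and 0.90 to 0.91 in simulation with correlation 0 to 0.5, whatever the sample size. With IOP tested at three postoperative visits as well as CEC, independence gives 0.95⁴ ≈ 0.81.
- True CEC difference of 5 points, equal to the margin (SD 12.5): the product still passes about 78–79% of the time at 14 per arm and 74–75% at 18.
- True CEC difference of 10 points: about 44–45% and 33–34%.

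**5. IOP precision.** The 90% CI half-width for a difference in means is t₀.₉₅ × √(2/n) × SD. At 14 per arm this is 1.706 × 0.378 = 0.64 × SD; at 18 it is 1.691 × 0.333 = 0.56 × SD. For an assumed SD of 3–5 mmHg, that is 1.9–3.2 and 1.7–2.8 mmHg.

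**The case against.** The best defence is that the plan is open about what it did. Section 10.2.2 says that the calculation used the CEC decrease, sections 4.1 and 4.2 call the trial a pilot, and section 10.1.4 is a replacement rule that quotes no power. No sentence claims 80% for the two outcomes together. That is true, but section 10.1.4 does say that the number serves the study objective, and the objective and pass rule cover IOP as well. A pilot that states a power, a required number and a pass/fail safety verdict can be held to them.

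Three stronger readings are tempting and should not be adopted.

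- A reader might take the earlier comparator trial in section 2.2.2 (IOP of 30 mmHg or more: "the incidence of this AE was 10.5% in the Healon® EndoCoat group and 7.5% in the Viscoat® group"; δ = 0.13), work out one-sided power of about 30% at 14 per arm and 35% at 18, and treat that as a ceiling on joint power. The documents do not support this. IOP here is a continuous primary outcome, 30 mmHg is only the adverse-event reporting threshold (section 7.4.4.2), and this protocol never adopts the 13-point margin. A one-sided calculation also does not match an equivalence hypothesis.
- A reader might take 64% as the trial's actual joint power. It rests on independence and on 80% for each outcome; the first is assumed, and the second is unsupported for IOP and wrong for CEC.
- A reader might infer that too few subjects make a safe verdict hard to reach. Under section 10.1.2 as written the reverse holds: identical products pass about 90% of the time, and fewer subjects make it easier for a worse product to pass.

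**Conclusion.** The point stands in this form. The sample size considers CEC only, the conclusion requires CEC and IOP, and neither the 80% nor the 28 evaluable subjects is supported for that conclusion. The loss in joint power cannot be quantified, because the documents give no IOP margin or SD; under an equivalence reading it can only be said that joint power is no higher than the lower of the two.

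The larger numerical fault is in the CEC calculation: 223 rather than 14 at the stated margin, taking p = p0 = 0.0697. Adding IOP to the calculation would not repair that, and correcting CEC would not supply the missing IOP planning. Under the difference-test rule actually written, the stated power describes nothing. The pass rates above cover only the statistical half of that rule, since a clinical difference is not defined.

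**What to change.** In sections 10.2.2 and 10.1.4:

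- State that the calculation considered CEC loss only, and delete the clause in 10.1.4 that ties the 28 subjects to the study objective.
- Withdraw the 80% for CEC at a 5% margin, or correct it. Stating only that the size was derived for CEC would leave a wrong figure in place.
- Then choose one of two courses. Either state that no power is claimed for IOP or for the joint rule; or pre-specify equivalence margins and assumed SDs for both outcomes, judge both by 90% confidence intervals in 10.1.2, and report the resulting joint power.
- Give the expected IOP precision as a 90% CI half-width of about 0.64 × SD at 14 per arm and 0.56 × SD at 18, with the assumed SD stated.

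The cost is a less favourable power statement and some redrafting. No extra patients or procedures are needed.

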2.2.1 Efficacy of the investigational product

The efficacy of various SH-containing OVDs has been established in several clinical studies. A multicenter, double-blind, randomized clinical study was conducted with the Healon® EndoCoat OVD, which contains the same concentration of SH as PRO-149, in 400 patients undergoing phacoemulsification and IOL implantation.

Two hundred patients were assigned to the Healon® EndoCoat group and 200 to the control group, corresponding to Viscoat®. Efficacy was measured by CEC protection. Healon® EndoCoat demonstrated non-inferiority when compared to Viscoat® in the CEC count from pre-surgery to 3 months post-surgery ($p < 0.0001$, 1-tailed t-test, $\delta = 5\%$). The mean percentage changes observed were -4.7% for Healon® EndoCoat and -7.0% for Viscoat® with a percentage point difference of 2.3 (90% confidence interval: [0.23, 4.33]). [21]

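### The 14 eyes per arm in section 10.2.2 do not follow from the stated 5% margin: the printed formula gives 223, and the claimed 80% power for 5% equivalence is absent

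*Combined protocol and SAP*

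**What the plan says.** Section 10.2.2 (Justification of the sample calculation) starts from a published comparison of 1%, 2% and 3% sodium hyaluronate OVDs, with endothelial cell losses of 18.46%, 18.03% and 6.97%. It then says: "The percentage decrease in dispersive OVD at 3% SH was considered". The working hypotheses are those of equivalence, with alpha 0.05, 80% power and "a test margin (δ) of 5" percent. A sample size formula and a power formula are printed; the comparison value p0 is defined but given no number. The conclusion is: "According to the previous calculation, the result was 14 cases (eyes) per arm". This is raised for 20% losses to 18 per arm, 36 in total.

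Section 10.1.4 relies on the result. It says that, to meet the study objective, "28 evaluable subjects (14 cases per arm) are required", and ties the replacement of subjects to falling short of that number.

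**The concern.** The section prints its formula and all but one of its inputs, so the reader can redo the sum, and the sum does not give 14. A margin of 5 percentage points on a value near 7% is tight, and 14 eyes per arm is far too few for it by any usual calculation.

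What is at stake is the meaning of the result. The protocol states an equivalence hypothesis (section 3.5), tells committees and the authority that the trial has 80% power to show equivalence within 5%, and treats 28 evaluable subjects as enough for the objective. If that power is not there, finding no difference at the end says little about whether the two devices agree to within the margin.

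**Working it through.** **Inputs (section 10.2.2).** Alpha 0.05, so z(0.95) = 1.645. Beta 0.20, entering the printed formula as z(1 - β/2) = z(0.90) = 1.282. p = 0.0697. δ = 0.05. No p0 is given; I assume p0 = p, the natural reading when no difference is expected.

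**1. The printed sample size formula.** n = p(1 - p) × [(z(0.95) + z(0.90)) / (|p - p0| - δ)]².
- p(1 - p) = 0.0697 × 0.9303 = 0.06484, and (1.645 + 1.282)² = 8.564.
- δ = 0.05: 0.06484 × 8.564 / 0.0025 = 222.1, so **223**.
- δ = 0.20: 0.06484 × 8.564 / 0.04 = 13.88, so **14**.

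The next step is consistent with the plan: 14 / (1 - 0.20) = 17.5, so 18.

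**2. The printed power formula.** 1 - β = 2[Φ(z - 1.645) + Φ(-z - 1.645)] - 1, with z = (|p - p0| - δ) / √(p(1 - p)/n).

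| n | δ = 0.05 | δ = 0.20 |
|---|---|---|
| 14 | -0.62 | 0.804 |
| 18 | -0.57 | 0.908 |
| 223 | 0.802 | 1.000 |

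A negative value means zero power.

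**3. Can another reading at δ = 0.05 give 14?** Using other normal quantiles for alpha and beta with p = p0 = 0.0697 gives 117 to 273. Pairing p and p0 over the loss figures in the documents (4.7%, 6.97%, 18.03%, 18.46%, and rounded 5% and 7%) gives a minimum of 50, at p = 0.047 and p0 = 0.1846. That pair differs by more than the margin, so it is not an equivalence scenario. With p = p0, 14 would need p of about 0.4%, a loss figure that does not appear in the documents.

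**4. The formula does not match the design.** It tests one sample against a fixed reference, whereas section 7.3 randomises 1:1 to two arms. The two-sample form doubles the number per arm: 2 × 222.1 = 444.2, so 445 at 5%; 2 × 13.88 = 27.8, so 28 even at 20%. Table 3 (section 7.4.4) classes the endothelial cell count as continuous. The 6.97% is a mean loss of cell density, not a share of subjects, so p(1 - p) is not its variance.

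**5. The continuous scale.** The protocol gives no SD. Section 2.2.1 reports, for 200 patients per arm, a 90% interval of 0.23 to 4.33 points for the difference in mean percentage change. Assuming equal SDs and all 200 analysed:
- SE = (4.33 - 0.23) / (2 × 1.645) = 1.246, and SD = 1.246 / √(2/200) = 12.46 points.
- Expected 90% half-width, t × 12.46 × √(2/n): 1.706 × 4.71 = 8.0 points at 14 per arm; 1.691 × 4.15 = 7.0 points at 18 per arm.
- Power of two one-sided tests at ±5 points with no true difference: below 0.1% at either size.
- Size for 80% power: 2 × (12.46 × 2.926 / 5)², about 107 per arm.

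Sensitivity at 14 per arm: SD 5 gives 65% power, SD 8 gives 6%, SD 10 gives 0.4%. For 80% power the SD must be no more than about 4.5 points at 14 per arm, or about 5 at 18.

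**The case against.** The best points on the other side are these.

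- **p0 is missing.** The figure of 223 therefore rests on p0 = p. Algebraically, p = 0.0697 with p0 near 0.32 also returns 14 at a 5% margin. That is correct, but such a pair is far outside the margin and appears nowhere in the documents. That 20% was entered as the margin is inferred from the match; the only 20% figures in the calculation are beta and the loss allowance. That 14 does not follow from 5% at any documented value needs no such inference.
- **The SD is borrowed.** It comes from a different comparison, measured at 3 months rather than day 29. This stands: on the continuous scale the exact shortfall depends on the SD. But the protocol offers none, and only an SD well under half of the one implied by its own cited study would rescue the claim.
- **223 and 445 are not true requirements**, since a proportion formula does not suit the endpoint. Agreed. They measure how far the printed calculation is from its stated answer, not how many subjects the trial needs.
- **It is a pilot, and its size resembles that of similar studies.** A pilot may be small, and nothing here asks for more subjects. That does not support a stated 80% power, nor the use of 14 per arm in section 10.1.4 as the number required.
- **No planned test uses the margin.** Section 10.1.2 specifies difference tests and calls the product safe if none is found. That is a separate defect, and correcting the sample size text will not cure it.

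**Conclusion.** The concern holds. With the protocol's own alpha, power, planning value and 5% margin, and p0 = p, the printed formula gives 223, about 16 times the stated 14, and the printed power equation gives zero power at 14 or 18. A margin of 20 points reproduces 14. That would be wider than the 11.5-point gap between the best and worst OVD in the planning source (18.46 - 6.97 = 11.49), though the protocol does not state such a margin.

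On the appropriate continuous scale the conclusion is the same for an SD near 12.5 points. It weakens only if the SD is about 5 points or less, which nothing in the documents supports. The claim of 80% power for 5% equivalence should not stand, and it must be fixed because section 10.1.4 treats the resulting number as sufficient for the objective.

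**What to change.** Rewrite section 10.2.2:
- Delete the statement that 14 per arm gives 80% power for equivalence at 5%, and drop the one-sample proportion formula.
- State that 18 per arm is a pilot size, and give the precision it delivers for the between-arm difference in mean percentage change in cell density: an expected 90% half-width of about ±7 points at 18 per arm and ±8 at 14, for an SD of 12.5, with a range of SDs and the source of each.
- If a margin is kept, state the power that 14 to 18 per arm has for it, using a two-sample formula for means with an explicit SD.

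Amend section 10.1.4 so that 28 evaluable subjects are no longer described as what the objective requires. If replacement of subjects stays tied to a number, describe it as a pilot target.

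The cost is rewording two sections and stating a less favourable figure. No subjects, visits or procedures are added.
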